5.5.1. Planned Unblinding

Pfizer will release unblinding information to the investigators after all subjects have completed Visit 5 and will inform the investigators prior to Visit 7 which subjects may be invited to progress to Stage 2. Additional information is included in the SRM.

The booster vaccination will be open-label.

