Subjects from both the ACWY-naïve and ACWY-experienced strata, approximately 132 from each of Groups 1 and 3 and approximately 65 from each of Groups 2 and 4, will participate in Stage 2. Stage 1 will be observer-blinded and Stage 2 will be open-label. Investigators will be informed if a subject can be screened for Stage 2 based on a randomly generated list of eligible subjects and a randomly generated backup list to allow for replacement of subjects who decline participation in Stage 2 or are deemed ineligible after screening at Visit 7.

Visit 7 and Visit 8 should be conducted within no less than 30 days of each other. If Visit 7 cannot be conducted within the protocol-defined visit window, Visit 7 can be omitted and Visit 8 performed directly.

6.3.1. Visit 7 (336 to 694 Days After Visit 3), Antibody Persistence Blood Draw 1

- Obtain written informed consent, and assent if applicable, before performing further study-specific procedures. The date of informed consent will be recorded on the CRF.
- Ensure that the subject continues to be eligible for the study, meets none of the withdrawal criteria as described in [Section 6.5](#), and meets none of the temporary delay of blood draw criteria as described in [Section 4.4](#).
- Record nonstudy vaccinations as described in the Concomitant Treatment(s) section ([Section 5.11](#)).
- Collect a blood sample (approximately 20 mL).
- Record concomitant medications used to treat AEs as described in the Concomitant Treatment(s) section ([Section 5.11](#)).
- Schedule an appointment for the next visit and confirm that it is scheduled within the time window per protocol.
- Complete the source documents.
- Complete the CRFs.

6.3.2. Visit 8 (700 to 756 Days After Visit 3), Antibody Persistence Blood Draw 2

- Ensure that the subject continues to be eligible for the study, meets none of the withdrawal criteria as described in [Section 6.5](#), and meets none of the temporary delay of blood draw criteria as described in [Section 4.4](#).
- Record nonstudy vaccinations as described in the Concomitant Treatment(s) section ([Section 5.11](#)).
- Collect a blood sample (approximately 20 mL).
- Record any AEs and research-related injuries (RRIs) occurring within 48 hours after the Visit 7 blood draw as described in [Section 8](#).
- Record concomitant medications used to treat AEs as described in the Concomitant Treatment(s) section ([Section 5.11](#)).

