9.6. Modified Intent-to-Treat (mITT) Population

All randomized subjects who have at least 1 valid and determinate MenB or MenA/C/W/Y assay result available at any time point from Visit 1 to Visit 4 will be included in the mITT population for Stage 1. This will be the primary immunogenicity population for the analyses of the secondary endpoints related to ACWY endpoints in Stage 1.

The mITT population for Stage 2 is defined as all subjects who signed informed consent at Visit 7 and who have at least 1 valid and determinate MenB or MenA/C/W/Y assay result available in Stage 2.

The mITT populations will be used for the evaluation of the primary, secondary, and exploratory immunogenicity endpoints, and subjects will be analyzed according to the investigational product to which they were randomized. Endpoints to assess antibody persistence will include subjects in the Stage 2 mITT population.

Subjects included in the sentinel cohort will be included in the Stage 1 mITT population for immunogenicity analyses.

A booster mITT immunogenicity population will also be defined for supportive analyses for booster endpoints. This population will consist of subjects who received a booster vaccination and who have any booster immunogenicity data.

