9.7. Safety Analysis Set

The safety population will be used for all safety analyses. The safety population for Stage 1 will include all subjects who have received at least 1 dose of investigational product during Stage 1 and for whom safety data are available. The safety population for Stage 2 will include all subjects who received the booster vaccination and for whom safety data are available. For the safety analysis, subjects will be analyzed according to the investigational product received. Additionally, a persistence safety population will include all subjects who signed the informed consent to participate in Stage 2.

Separate safety populations will be defined for each vaccination visit and follow-up phase: Vaccination 1, Vaccination 2, follow-up phase for Stage 1, booster vaccination visit, and follow-up phase for Stage 2. These populations are detailed below.

1. Vaccination 1 safety population: This population will include all subjects who received the first dose of investigational product (MenABCWY + saline or bivalent rLP2086 + MenACWY-CRM) at Visit 1, and for whom safety information from Visit 1 to before Visit 3 is available.
2. Vaccination 2 safety population: This population will include all subjects who received the second dose of investigational product (MenABCWY or bivalent rLP2086) at Visit 3, and for whom safety information from Visit 3 up to and including Visit 4 is available.
3. Follow-up safety population for Stage 1: This population will include all subjects who received at least 1 dose of investigational product and for whom safety information is available from after Visit 4 up to and including Visit 5. Subjects who received the wrong investigational product and are followed for 6 months for safety will not be included in this population.
4. Booster vaccination safety population: This population will include all subjects who received the booster dose of investigational product (MenABCWY or bivalent rLP2086) at Visit 10, and for whom safety information from Visit 10 up to and including Visit 11 is available.
5. Follow-up safety population for Stage 2: This population will include all subjects who received the booster dose of investigational product and for whom safety information is available from after Visit 11 up to and including Visit 12. Subjects who received the wrong investigational product and are followed for 6 months for safety will not be included in this population.

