##### **4.1. Full Analysis Set**

A Stage 1 intent-to-treat (ITT) population will be defined and will include all subjects who are randomized at Visit 1. A Stage 2 ITT population will be defined as all subjects who signed the ICD at Visit 7.

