##### **4.2. Modified Intent-to-Treat Population**

All randomized subjects who have received at least 1 study vaccination and who have at least 1 valid and determinate primary strain MenB or MenA/C/W/Y assay result available at any time point from Visit 1 to Visit 4 will be included in the modified intent-to-treat (mITT) population for Stage 1.

The mITT population for Stage 2 is defined as all subjects who signed the ICD at Visit 7 and who have at least 1 valid and determinate primary strain MenB or MenA/C/W/Y assay result available in Stage 2.

The mITT population will be analyzed according to the investigational product to which subjects were randomized (see handling of mis-stratified subjects in [Section 4.5](#)).

Subjects included in the pilot cohort will be included in the Stage 1 mITT population for immunogenicity analyses.

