The Stage 2 mITT population is the analysis population for assessing the secondary immunogenicity endpoint of antibody persistence.

The Stage 1 mITT population will also be used to perform additional analysis for serogroup B endpoint assessment in Stage 1.

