#### 4.4. Safety Analysis Set

The safety population will be used for all safety analyses and will be defined for each stage of the study.

1. The safety population for Stage 1 will include subjects who have received at least 1 dose of investigational product during Stage 1 and for whom safety data are available.
2. The safety population for Stage 2 will include subjects who received the booster vaccination and for whom safety data are available.

For the safety analysis, subjects will be analyzed according to the investigational product received.

Separate safety populations will be defined for each vaccination visit: Vaccination 1, Vaccination 2, follow-up phase for Stage 1, persistence phase, booster vaccination visit, and follow-up phase for Stage 2.

1. Vaccination 1 safety population: this population will include subjects who receive the first dose of investigational product (MenABCWY+saline or bivalent rLP2086+MenACWY-CRM) at Visit 1, and for whom safety information from Visit 1 to prior to Visit 3 is available.
2. Vaccination 2 safety population: this population will include subjects who receive the second dose of investigational product (MenABCWY or bivalent rLP2086) at Visit 3, and for whom safety information from Visit 3 up to and including Visit 4 is available.
3. Follow-up safety population for Stage 1: this population will include subjects who receive at least 1 dose of investigational product and for whom safety information is available from after Visit 4 up to and including Visit 5.
4. Persistence safety population: this population will include all subjects who signed the ICD at Visit 7. This population is analogous to the Stage 2 ITT population.
5. Booster vaccination safety population: this population will include all subjects who receive the booster dose of investigational product (MenABCWY or bivalent rLP2086) at Visit 10, and for whom safety information from Visit 10 up to and including Visit 11 is available.
6. Follow-up safety population for Stage 2: this population will include all subjects who receive the booster dose of investigational product and for whom safety information is available from after Visit 11 up to and including Visit 12.
7. Booster safety population: this population will include all subjects who receive the booster dose of investigational product at Visit 10, and for whom safety information from Visit 10 up to and including Visit 12 is available.

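### Three Stage 2 analysis sets depend on consent signed at a visit that may be skipped, and no planned analysis shows how nonstudy meningococcal vaccines affect persistence at Visits 7 to 9

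*SAP*

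**What the plan says.** **Set definitions.** SAP 4.1: "A Stage 2 ITT population will be defined as all subjects who signed the ICD at Visit 7". SAP 4.2: "The mITT population for Stage 2 is defined as all subjects who signed the ICD at Visit 7", with at least one valid Stage 2 assay result. SAP 4.4, on the safety set for the persistence phase: "this population will include all subjects who signed the ICD at Visit 7. This population is analogous to the Stage 2 ITT population". Protocol 9.6 defines the Stage 2 mITT in the same way, as "all subjects who signed informed consent at Visit 7". Protocol 9.7 differs: "a persistence safety population will include all subjects who signed the informed consent to participate in Stage 2", with no visit named.

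**Visit path.** Protocol 6.3 and footnote a of the Stage 2 schedule in both documents state: "If Visit 7 cannot be conducted within the protocol-defined visit window, Visit 7 can be omitted and Visit 8 performed directly". Both schedules mark Stage 2 consent at Visit 7 only, and the Visit 8 procedures in Protocol 6.3.2 contain no consent step.

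**Persistence analysis.** SAP 4.3: "The Stage 2 mITT population is the analysis population for assessing the secondary immunogenicity endpoint of antibody persistence". The persistence rows of SAP Table 19 name no other set.

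**Nonstudy meningococcal vaccines.** Protocol 5.11.1 prohibits them throughout the study. Under Protocol 5.11, names and dates go on the CRF up to Visit 11. Protocol 6.5 leaves withdrawal to judgment. SAP 6.6.1 and 6.6.4 provide listings of protocol deviations and, for Stage 2, of nonstudy vaccines. SAP 6.4 says an analysis may be done without subjects vaccinated between Visits 1 and 4, as a follow-on to the MenA/C/W/Y endpoints.

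**The concern.** Two gaps affect the same persistence tables.

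First, the set definitions do not fit a visit path that the protocol permits. A subject who enters Stage 2 at Visit 8 and provides valid titers has complied fully, yet fails the entry condition for the Stage 2 ITT, the Stage 2 mITT and the SAP's persistence safety population. Protocol 9.7 would include that subject in the persistence safety population, so the two documents can give one named population different members. It is also the denominator for the blood-draw events in SAP 6.7.2.3.

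Second, a subject given a nonstudy meningococcal vaccine before a Stage 2 draw stays in the Stage 2 mITT, and the new response is counted as persistence of the study vaccine. The other sets guard against this: the Stage 1 evaluable population excludes recipients of prohibited vaccines, and the booster evaluable population excludes major violations. Exposure is plausible. Subjects enroll from age 10, Protocol 1.2.1 notes a US booster recommendation at 16, and Stage 2 is open-label. The listings show who was vaccinated, but not how far the proportions move.

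**Working it through.** **Stage 2 size.** 2 × 132 + 2 × 65 = 394, which reproduces the figure in Protocol 3.3.

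**Part 1: who could be left out**

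1. The Visit 7 window is 336 to 694 days after Visit 3: 694 − 336 + 1 = 359 days.
2. Under Protocol 5.5.1 the sponsor will "release unblinding information to the investigators after all subjects have completed Visit 5" and then say who may progress. The last subject's Visit 5 falls 168 to 196 days after that subject's Visit 3. Let X be the number of days by which a given subject's Visit 3 precedes the last subject's, and L the release lag. The given subject is already past day 694 at release if X + (168 to 196) + L ≥ 695.
   - L = 0: X ≥ 499 to 527 days.
   - L = 90 (assumption): X ≥ 409 to 437 days.
3. The enrollment span is not given, so this count cannot be derived. Other omissions would come from scheduling. If 2%, 5%, 10% or 20% of the 394 omitted Visit 7 (assumptions), about 8, 20, 39 or 79 would fail the literal definition.
4. A subject left out has no Visit 7 titer. Only Visits 8 to 10 and the Visit 1 and Visit 4 reference columns change.
5. Shift in an illustrative estimate near 70%. The extremes are that all those left out were responders (estimate falls) or all were nonresponders (estimate rises):

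| Group | Full set | Left out | Lowest | Highest | Shift (points) |
|---|---|---|---|---|---|
| Group 2 or 4 | 46/65 = 70.8% | 1 | 45/64 = 70.3% | 46/64 = 71.9% | −0.5 to +1.1 |
| Group 2 or 4 | 46/65 = 70.8% | 5 | 41/60 = 68.3% | 46/60 = 76.7% | −2.4 to +5.9 |
| Group 1 or 3 | 92/132 = 69.7% | 1 | 91/131 = 69.5% | 92/131 = 70.2% | −0.2 to +0.5 |
| Group 1 or 3 | 92/132 = 69.7% | 5 | 87/127 = 68.5% | 92/127 = 72.4% | −1.2 to +2.7 |
| Groups 2+4 | 91/130 = 70.0% | 5 | 86/125 = 68.8% | 91/125 = 72.8% | −1.2 to +2.8 |
| Groups 1+3 | 185/264 = 70.1% | 5 | 180/259 = 69.5% | 185/259 = 71.4% | −0.6 to +1.4 |

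The single groups apply to the MenA/C/W/Y endpoints and the combined groups to MenB.

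**Part 2: bias from nonstudy vaccines**

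Let c be the share vaccinated against the serogroup before the draw, and p the proportion that would otherwise meet the threshold. Suppose recipients have the same underlying p as the rest of the group. If every recipient responds, the observed proportion is (1 − c)p + c = p + c(1 − p), so the upward bias is at most c(1 − p). The documents give neither c nor p:

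| p | c = 1% | c = 5% | c = 10% | c = 20% |
|---|---|---|---|---|
| 30% | 0.7 | 3.5 | 7.0 | 14.0 |
| 50% | 0.5 | 2.5 | 5.0 | 10.0 |
| 70% | 0.3 | 1.5 | 3.0 | 6.0 |
| 90% | 0.1 | 0.5 | 1.0 | 2.0 |

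(percentage points)

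For scale, the exact 95% interval for 46/65 is 58.2% to 81.4% (half-width 11.6 points) and for 92/132 it is 61.1% to 77.4% (half-width 8.1). At p = 50% the half-widths are 12.7 and 8.8.

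**The case against.** **On the sets.** The wording is most naturally shorthand for Stage 2 consent, since the schedules put that consent at Visit 7 and Protocol 9.7 states the broader meaning outright. Protocol 6.1 requires written consent before any study procedure, so a Visit 8 entrant must consent whether or not Protocol 6.3.2 lists the step. This probably describes the intent, and it means there is no consent gap. It does not change the definitions: no text says the phrase is shorthand, and Protocol 9.6 and 9.7 differ from each other. The number affected is also likely to be small, given the 359-day window, and the widest shift above comes from the smallest groups. Both points stand.

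**On the vaccines.** An mITT set is a legitimate choice for a descriptive endpoint. Nonstudy vaccines are recorded at each blood-draw visit, bear on continued eligibility and are listed. Visit 10 titers are also reported on the booster evaluable population, which is cleaner. SAP 6.4 refers to Table 19, which includes MenA/C/W/Y persistence rows, so an optional rerun could reach them. The choice of set and the Visit 10 coverage stand. But the booster tables do not include Visits 7 to 9, and the optional rerun would cover only vaccines received by Visit 4. Visit 9 falls 1064 to 1120 days after Visit 3, so most of the relevant exposure time lies outside that limit.

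**Conclusion.** Both parts hold, and both are minor. Followed as written, the SAP drops compliant Visit 8 entrants from the Stage 2 ITT, the Stage 2 mITT and the persistence safety population, and it contradicts the protocol on the last of these. Nothing planned shows the effect on the Visits 7 to 9 results of nonstudy meningococcal vaccines received after Visit 4.

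In size, losing a handful of subjects moves an estimate near 70% by one to a few points, with an extreme of +5.9 when 5 of 65 are lost and all were nonresponders. Vaccine bias stays well inside the confidence interval when c is 5% or less. It becomes comparable to the interval half-width only when c is 10% to 20% and persistence is low to middling.

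The omission rate, the vaccination rate, the persistence level and the 90-day lag are all assumptions. Persistence is descriptive, and the coprimary analysis is unaffected. The booster populations carry no Visit 7 condition.

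**What to change.** 1. In SAP 4.1, 4.2 and 4.4 and Protocol 9.6, replace the Visit 7 condition with: signed the Stage 2 ICD at Visit 7, or at Visit 8 if Visit 7 was omitted. Check that Protocol 9.7 then gives the same persistence safety population. List the consent step at Visit 8 for these subjects in Protocol 6.3.2 and both schedules.

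2. Keep the Stage 2 mITT persistence analysis and the Stage 1 wording of SAP 6.4 as they are. Add one prespecified sensitivity analysis covering Visits 7 to 10: set to missing each hSBA result for a serogroup drawn after a nonstudy vaccine containing that serogroup. Apply it by CRF vaccine date, not by deviation status. Including Visit 10 keeps the persistence series on one rule.

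3. Reconcile Protocol 5.11.1, which prohibits meningococcal vaccines throughout, with the outbreak provision in 5.11.2, which does not repeat that exception. The sensitivity analysis works however this is settled, because it does not depend on whether receipt counts as a deviation.

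The cost is a few sentences in the SAP, a short protocol clarification and one extra table with slightly fewer titers. The vaccine names and dates are already collected.

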##### **4.3. Per-Protocol Analysis Set (Evaluable Immunogenicity Population)**

The per-protocol analysis set will be referred to as the evaluable immunogenicity population, which is the primary population for the primary immunogenicity objective assessments.

All randomized subjects who are included in the Stage 1 mITT population as well as who meet the following criteria will be included in the Stage 1 evaluable immunogenicity population. The Stage 1 MenB strain secondary immunogenicity endpoints will also be reported on this population.

1. Were randomized to the study group of interest.
2. Were eligible throughout the study, ie, fulfilling all of the inclusion criteria and none of the exclusion criteria at each visit where eligibility criteria were collected and confirmed.
3. Received all investigational products as randomized.
4. Had blood drawn for assay testing within the required time frames at Months 0 (Visit 1: before Vaccination 1) and 7 (Visit 4: 1 month after Vaccination 2: window 28-42 days).
5. Had valid and determinate assay results for the proposed analysis.
6. Had received no prohibited vaccines or treatment.
7. Had no other major protocol violations as determined by the sponsor's global medical monitor.

The booster evaluable immunogenicity population includes subjects who were eligible for the study (ie, meet all Stage 1 eligibility criteria as well as continually meeting Stage 2 eligibility criteria), received a booster dose as intended (the same vaccine as they received in Stage 1), had blood drawn for assay testing within the required time frame at Month 55 (Visit 11), and had a valid and determinate MenB or MenA/C/W/Y assay result after the booster dose, as well as no major protocol violations as determined by the sponsor's global medical monitor.

The evaluable immunogenicity population is the analysis population for assessing the primary immunogenicity objective. Specifically, this includes the evaluable immunogenicity US subset that would be used to assess the primary objective of the study. The evaluable immunogenicity population is also the analysis population for assessing the secondary immunogenicity MenB endpoint in Stage 1.

The Stage 1 mITT population is the analysis population for assessing the ACWY endpoint in Stage 1.

The booster evaluable immunogenicity population is the analysis population for assessing the ACWY and serogroup B endpoints following the booster dose.

The Stage 2 mITT population is the analysis population for assessing the secondary immunogenicity endpoint of antibody persistence.

The Stage 1 mITT population will also be used to perform additional analysis for serogroup B endpoint assessment in Stage 1.

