5.11.1. Prohibited During the Study

- Receipt of any blood products, including immunoglobulin.
- Nonstudy meningococcal vaccines or vaccines containing 1 or more ABCWY group are prohibited throughout the course of the study.
- Nonlive or live nonstudy vaccines are not permitted within 14 and 28 days, respectively, of any study vaccination.
- Vaccine containing all or individual antigens included in Tdap vaccine are not permitted within 28 days of any study vaccination.
- Intramuscular/sublingual allergen immunotherapy is not permitted within 14 days of any study vaccination.
- Systemic (oral, intravenous, or intramuscular) corticosteroid therapy within 28 days of any study vaccination.

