### **6.2. Secondary Endpoints**

#### **6.2.1. Secondary Immunogenicity Endpoints**

Stage 1 secondary immunogenicity endpoint data will be summarized according to randomized vaccine for subjects included in the Stage 1 mITT population. The Stage 1 MenB strain endpoints will also be summarized on the Stage 1 evaluable immunogenicity population. Vaccine misallocations concerning vaccine history and ACWY strata as described in [Section 4.5](#) will apply.

Persistence will be summarized for subjects included in the Stage 2 mITT populations. Booster vaccination will be summarized for subjects included in the booster evaluable immunogenicity population.

For immunogenicity endpoints relating to MenACWY strains, subjects in the experienced ACWY stratum who received monovalent C vaccine will only contribute to the serogroup C analyses, while subjects who received quadrivalent vaccine will contribute to the full serogroup analyses.

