**Table 19. Analysis for MenABCWY Immune Response Secondary Objectives**

Stage of Study	Objective	Randomized Groups	Analysis Time Point	Analysis Population(s)	Strain/Serogroup	Analysis Endpoint	
	ABCWY response after MenABCWY vs MenACWY-CRM/bivalent rLP2086 at all blood sampling time points prior to booster dose (during Stage 1)	1+3 vs 2+4	Visits 1, 2, 3, and 4 (baseline, post-Vaccination 1 blood draw, Vaccination 2, post-Vaccination 2 blood draw)	Stage 1 evaluable immunogenicity, Stage 1 mITT	PMB80(A22) PMB2001(A56) PMB2948(B24) PMB2707(B44)	Subjects with hSBA titer $\geq$ LLOQ for each strain Subjects with hSBA titer $\geq$ 1:4, $\geq$ 1:8, $\geq$ 1:16, $\geq$ 1:32, $\geq$ 1:64, and $\geq$ 1:128 for each strain hSBA GMTs for each strain	
		1 vs 2 and 3 vs 4	Visits 1, 2, 3, and 4 (baseline, post-Vaccination 1 blood draw, Vaccination 2, post-Vaccination 2 blood draw)	Stage 1 mITT	MenA MenC MenW MenY	Subjects with hSBA titer $\geq$ 1:8 (or LLOQ, whichever is higher) for each serogroup Subjects with hSBA titer $\geq$ 1:4, $\geq$ 1:8, $\geq$ 1:16, $\geq$ 1:32, $\geq$ 1:64, and $\geq$ 1:128 for each serogroup hSBA GMTs for each serogroup	
Persistence	ABCWY response after MenABCWY vs MenACWY-CRM/bivalent rLP2086 at all blood sampling time points prior to booster dose (during Stage 2)	1+3 vs 2+4	Visits 1, 4, 7, 8, 9, and 10 (baseline, post-Vaccination 2 blood draw, antibody persistence blood draws 1-3, before booster vaccination)	Stage 2 mITT	PMB80(A22) PMB2001(A56) PMB2948(B24) PMB2707(B44)	Subjects with hSBA titer $\geq$ LLOQ for each strain	
		1 vs 2 and 3 vs 4	Visits 1, 4, 7, 8, 9, and 10 (baseline, post-Vaccination 2 blood draw, antibody persistence blood draws 1-3, before booster vaccination)	Stage 2 mITT	MenA MenC MenW MenY	Subjects with hSBA titer $\geq$ 1:8 (or LLOQ, whichever is higher) for each serogroup	

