#### 6.4. Additional Immunogenicity Analysis

Subjects who received prior polysaccharide meningococcal vaccine or subjects whose prior ACWY history is unknown are included in the mITT population as described in [Section 4.5](#). Additional sensitivity analyses of the secondary immunogenicity endpoints relating to MenA/C/W/Y strains described in [Table 19](#) may be performed by removing these subjects from the mITT population. Similar additional analyses may be done by removing from the analyses those subjects who received nonstudy meningococcal vaccines at any point between Visits 1 and 4.

An additional supportive analysis using the evaluable population (US and overall) is planned for the composite response (described in [Section 5.2.1.2](#)). For this supportive analysis, subjects with an assay titer < LLOQ for any of the 4 primary MenB strains will be defined as a nonresponder (composite response = 0) rather than have the status of missing.

Positive predictive value (PPV) analyses of secondary strain response for a given primary strain response within the primary strain subfamily will be performed at 1 month after the second vaccination using the evaluable immunogenicity population. For a specific time point, the PPV between a primary and secondary strain will be defined as follows: for the subjects who had titers  $\geq$  LLOQ for the primary strain, the percentage of subjects who have titers  $\geq$  LLOQ for the secondary strain. The calculation will require available data for both the primary and secondary strains.

Additional analyses may be performed to investigate the relationship of hSBA titers between the pre-booster dose time point and the post-booster dose time point for MenA, MenC, MenW, and MenY test strains separately for MenACWY-naïve and -experienced MenABCWY and Menveo groups. Scatterplots (with Pearson correlation coefficients) of pre-booster dose hSBA titers versus fold-rises from the pre-booster dose time point to the post-booster dose time point using the booster evaluable immunogenicity population will be provided. Similar analyses may be performed for Dose 1 and Dose 2 using the Stage 1 mITT population.

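### Antibody persistence (Visits 7 to 10) has no committed analysis that sets aside titers drawn after a nonstudy meningococcal vaccine

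*SAP*

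**What the plan says.** The protocol and SAP agree on the persistence population. SAP 4.3: "The Stage 2 mITT population is the analysis population for assessing the secondary immunogenicity endpoint of antibody persistence". Protocol 9.6: "Endpoints to assess antibody persistence will include subjects in the Stage 2 mITT population". SAP 6.2.1: "Persistence will be summarized for subjects included in the Stage 2 mITT populations". Both persistence rows of SAP Table 19 (MenB, and MenA/C/W/Y) list only this set, for time points that include "antibody persistence blood draws 1-3, before booster vaccination". SAP 4.2 admits subjects who consented at Visit 7 and "who have at least 1 valid and determinate primary strain MenB or MenA/C/W/Y assay result available in Stage 2". It sets no condition on prohibited vaccines or protocol deviations.

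Protocol 5.11.1: "Nonstudy meningococcal vaccines or vaccines containing 1 or more ABCWY group are prohibited throughout the course of the study". Protocol 5.11.2, however, allows nonstudy vaccines given in a disease outbreak, and that item makes no exception for meningococcal vaccines.

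SAP 6.4 contains the only analysis that deals with such vaccines. It first describes "Additional sensitivity analyses of the secondary immunogenicity endpoints relating to MenA/C/W/Y strains" in Table 19, and then says that similar "analyses may be done by removing from the analyses those subjects who received nonstudy meningococcal vaccines at any point between Visits 1 and 4".

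**The concern.** A titer drawn after re-vaccination measures the response to the new dose, not what remains from the study vaccine. It can move a subject from below to above 1:8 (ACWY) or the LLOQ (MenB). This happens only if the vaccine received contains that serogroup and the subject would otherwise have been below the threshold. The error therefore goes one way: persistence looks better than it is.

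Exposure is plausible for ACWY. Protocol 1.2.1 cites a routine US ACWY booster at age 16. Subjects enroll from age 10, mostly at US sites, and Stage 2 lasts about 4 years, so some can pass age 16 during follow-up. Protocol 1.2.1 describes the group B recommendation for at-risk individuals, so MenB re-vaccination is less likely.

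Elsewhere the SAP treats the problem as real: the Stage 1 evaluable population excludes subjects who received prohibited vaccines. Persistence, which has the longest exposure, has no counterpart.

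**Working it through.** **Stage 2 size.** Protocol 3.3 gives about 394 subjects: 2 × 132 + 2 × 65 = 264 + 130 = 394, which reproduces. MenB uses the combined groups (264 and 130); ACWY uses single groups (132 and 65).

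**Time not covered by SAP 6.4.** From the visit windows in the Schedule of Activities:

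- Visit 1 to Visit 4: 173 + 28 = 201 to 194 + 42 = 236 days.
- Visit 4 to Visit 9: 1064 − 42 = 1022 to 1120 − 28 = 1092 days.
- Visit 4 to Visit 10: 1428 − 42 = 1386 to 1484 − 28 = 1456 days.
- Share of Visit 1 to Visit 10 that SAP 6.4 covers: 201/(201 + 1456) = 12.1% to 236/(236 + 1386) = 14.5%.
- After the Visit 7 screen: to Visit 9, 1064 − 694 = 370 to 1120 − 336 = 784 days; to Visit 10, 1428 − 694 = 734 to 1484 − 336 = 1148 days.

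**Size of the shift.** Let f be the share re-vaccinated with a vaccine containing the serogroup before the draw, p the true persistence proportion (taken as the same in re-vaccinated and other subjects), and s the proportion at or above the threshold after re-vaccination. The reported proportion is (1 − f)p + fs, so shift = f × (s − p). None of these inputs is in the documents; all are assumed.

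| f | p | s | Shift (points) |
|---|---|---|---|
| 5% | 80% | 95% | 0.05 × 0.15 = 0.75 |
| 5% | 40% | 100% | 0.05 × 0.60 = 3.0 |
| 10% | 80% | 95% | 0.10 × 0.15 = 1.5 |
| 10% | 40% | 100% | 0.10 × 0.60 = 6.0 |
| 10% | 30% | 100% | 0.10 × 0.70 = 7.0 |

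**Scale against sampling error.** Clopper-Pearson 95% half-widths at p = 40% are 6.07 points (n = 264), 8.7 (n = 132) and 12.4 (n = 65). At p = 30% they are 5.7, 8.1 and 11.8. The 10% shift is thus just inside the half-width for n = 264 at 40% persistence (6.0 against 6.07) and outside it at 30% (7.0 against 5.7).

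**Unequal re-vaccination.** If f were 5% in one arm and 10% in the other, with p = 50% and s = 100% in both, the spurious difference would be (0.10 − 0.05) × (1.00 − 0.50) = 2.5 points.

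**Precision cost of removal.** At p = 50% and f = 10%, the half-width goes from 8.8 to 9.3 points (n from 132 to 119) and from 12.7 to 13.3 points (n from 65 to 59).

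**The case against.** The strongest reply is that conduct and existing outputs already handle this, and that analysing every consenting subject with a valid result is a legitimate choice for descriptive endpoints. Taking the safeguards in turn:

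- **Prohibition (Protocol 5.11.1).** It limits how often this happens, but does not remove a titer once drawn. The outbreak allowance in 5.11.2 also leaves a possible route.
- **Eligibility checks.** Visit 7 is a screen with a backup list, and eligibility is confirmed again at Visits 8 to 10. This should remove some affected subjects. But withdrawal under Protocol 6.5 is discretionary. The ACWY exclusions either count more than one dose or are dated from randomization, so a single nonstudy dose given later to a naive subject is not clearly caught.
- **Listings (SAP 6.6.1 and 6.6.4).** Stage 2 nonstudy vaccines and protocol deviations are listed, so a count can be derived. A listing does not show the effect on the proportions.
- **Visit 10 in the booster tables.** Visit 10 values are also tabulated in the booster evaluable population, which requires continuing eligibility and no major violations. This is a partial check, for boosted subjects only. Visits 7 to 9 have none.
- **SAP 6.4 itself.** Because it refers to Table 19, its optional analysis could reach the ACWY persistence rows. Even so, it would remove only subjects vaccinated between Visits 1 and 4, and would not reach MenB.

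The reply stands in part: the gap is narrowed, and the rerun may prove unnecessary if nobody is affected. It does not stand as a correction of the persistence proportions.

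**Conclusion.** The gap is real and of low priority. No planned persistence analysis sets aside titers drawn after a nonstudy meningococcal vaccine given after Visit 4, and none does so for MenB at any time. The endpoints are secondary and descriptive (Protocol 9.2.2), and the primary objective is untouched.

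The direction of any bias is upward. The illustration gives 0.75 to 6.0 points over the assumed ranges and more at lower persistence; it rests wholly on those assumptions, and applying the same rates to MenB has less support than applying them to ACWY.

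A reader might infer four stronger things that the documents do not support:

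- **That reported persistence will be materially inflated.** No re-vaccination rate is given, so the actual bias is unknown and could be nil.
- **That the bias can be ignored because it is smaller than the confidence interval.** That holds only for some inputs, and the interval does not account for a one-directional error.
- **That the arms are affected equally, or that the comparison is known to be distorted.** Neither is shown. Groups 1 and 3 receive two ACWY-containing study doses in Stage 1 and Groups 2 and 4 receive one; assignments are released to investigators after all subjects complete Visit 5, and Stage 2 is open-label. A difference in ACWY re-vaccination therefore cannot be ruled out.
- **That the Stage 2 mITT is the wrong main population.** It is a defensible choice, stated consistently in both documents.

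**What to change.** Keep the Stage 2 mITT as the main persistence analysis. Add one paragraph to SAP 6.4 that commits (*will*, not *may*) to a sensitivity analysis of the Table 19 persistence rows, ACWY and MenB. It should set to missing any titer drawn after the recorded date of a nonstudy vaccine containing the serogroup analysed, from Visit 1 through Visit 10, and keep that subject's earlier titers. Report the numbers of subjects and titers affected by group and visit. If there are none, say so and omit the rerun.

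No new data are needed: Protocol 5.11 and SAP 3.6.2 already have nonstudy vaccine names and dates on the CRF up to Visit 11. Sample size, alpha and the main analysis do not change. The costs are a few reruns, slightly fewer titers at later visits, and an assumption that re-vaccination is unrelated to titer, which should be stated with the result.
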